2. BACKGROUND INFORMATION

Multiple sclerosis (MS) is an autoimmune, inflammatory, demyelinating disease of the central nervous system (CNS) influenced by genetic susceptibility and some environmental factors not yet fully understood³. Relapsing forms of MS (RMS) are generally characterized by clearly defined periods of worsening neurological symptoms [i.e. relapse] followed by full or partial recovery [i.e. with sequelae and residual deficits upon recovery]. Relapsing forms of MS

include relapsing remitting or secondary progressive. In RMS, there is no clinically obvious disease progression during the periods between disease relapses⁴.

Relapses are typically treated with a high dose of glucocorticoids over a short period of time [3-5 days]. Certain immunomodulatory agents, including interferon beta preparations, glatiramer acetate, natalizumab, fingolimod, dimethyl-fumarate, alemtuzumab and teriflunomide, have shown beneficial effects for patients with RMS (decreased relapse rate and a slower accumulation of brain lesions on MRI). However, these treatments may be associated with significant toxicity and limited efficacy over time⁴.

2.1.Pathophysiology of Multiple Sclerosis and gut bacteria

The gut microbiome has recently emerged as a potential contributor to MS pathogenesis^{5,6}. Previously reviewed data from murine model of autoimmune demyelinating disease^{7,8} suggest that gut microbiota can powerfully modulate immune-mediated demyelination. Moreover, studies involving MS patients have shown that their microbial composition is different compared to healthy controls^{9,10,11} and this could be related to disease development and activity¹². Fecal microbial transplantation (FMT) from healthy donors is already used to restore normal fecal flora and treat colitis caused by *Clostridium difficile*. Therefore, we proposed that fecal microbial transplantation from a healthy donor could change the fecal flora composition of RMS patients, have a measurable effect on biomarkers of inflammation and possibly influence clinical or MRI disease activity.

We conducted a review about gut microbiome and MS accepted for publication (Mult Scler 2016 Dec 12. Breaking down the gut microbiome composition in multiple sclerosis).

2.2.Description of Fecal Microbial Transplantation

Fecal microbiota transplantation is the process of **fecal** bacteria transfer from a healthy donor into a recipient. The goal is to restore **colonic microflora** by transplanting healthy bacterial flora (e.g. by **enema, orogastric tube** or by mouth in the form of a capsule containing **freeze-dried** material)¹². For this study we selected the enema that is a lower risk procedure compared to an upper tract endoscopy and more easily accepted for patients than an oral capsule of fecal bacteria. An enema will be done to infuse the study treatment into the **lower bowel** through the **rectum** by a trained nurse.

2.3. Summary of literature on MS and Gut Microbiome

There is a growing body of evidence that gut microbiota goes beyond classical physiological functions such as vitamin production, digestion of nutrients, or protection against pathogens. Under normal physiological conditions, the human gut microbiota is a homeostatic ecosystem.

Disruption of this equilibrium can result in what is known as “dysbiosis” and has been associated with several conditions, such as gastrointestinal diseases, obesity, diabetes, chronic periodontitis, vaginosis, atopic diseases, non-alcoholic steatohepatitis, and Alzheimer’s disease¹³.

Some studies have shown that MS patients have an alteration in their microbiota composition compared to healthy individuals. In a pilot study of the gut microbial in MS, Cantarel et al. found decreased *Faecalibacterium* among seven RMS patients compared to eight controls¹⁴. Miyake et al. compared 20 Japanese RMS patients to 40 controls and similarly found that there was a depletion of species belonging to butyrate-producing *Clostridium* clusters XIVa and IV, including *Faecalibacterium prausnitzii* and *Eubacterium rectale*¹⁴, among MS patients. Chen et al. found depletion of the butyrate-producing family *Erysipelotrichaceae*, which belongs to *Firmicutes*, among 31 patients with RMS compared to 36 controls¹⁵. Interestingly, however, the authors also noted an increased abundance of *Blautia* and *Dorea* genera, both belonging to *Clostridium* cluster XIVa, among their RMS patients¹⁵. Tremlett et al. also noted a depletion of butyrate-producing *Faecalibacterium*, *Lachnospiraceae*, *Ruminococcaceae* and *Butyricimonas* among 18 cases of early pediatric MS compared to 17 controls¹⁶. Two observational studies, the first by Gandhi et al. and the second by Jangi et al., reproducibly identified a reduction in the *Butyricimonas* genus among MS patients, which belongs to the *Bacteroidetes* phylum but is capable of producing butyrate^{17,18}. In another pediatric study, Tremlett et al. followed 17 RRMS patients over a mean of 19.8 months and found that depletion of *Fusobacterium* genera, belonging to the *Fusobacteria* phylum, was associated with increased relapse risk¹⁹. Although presence of *Fusobacteria* has been associated with autoimmunity, including juvenile idiopathic arthritis and ulcerative colitis, *Fusobacterium* is also a butyrate producer²⁰⁻²². The depletion of butyrate-producing bacteria in MS suggests that this pro-inflammatory alteration of the gut microbiota may be linked to disease pathogenesis.

Rumah et al. identified the first RMS patient with epsilon toxin (ETX)-producing *C. perfringens* Type B in her GI tract²³. ETX is produced by *Clostridium perfringens* types B and D³⁵. It disrupts the blood-brain barrier and binds myelin, leading to its consideration as a potential MS trigger³⁵. The authors found reduced non-toxicogenic *Clostridium perfringens* Type A in the gut microbial of MS patients, and suggest this may create an ecological niche for ETX-producing *Clostridium perfringens*²⁴. Among their MS patients, 10% had antibodies specific to ETX in CSF and plasma compared to only 1% of controls, indicating increased immune system exposure to ETX among MS patients²⁴.

Furthermore, Miyake et al. found reductions of *Bacteroidetes*, including several *Bacteroides* species and *Prevotella copri*, among their RMS patients¹⁶. Similarly, Baum et al. compared 54 patients with MS to healthy controls and found reduced *Bacteroidaceae*, a family belonging to *Bacteroidetes*²⁶. Tremlett et al. also found decreased *Bacteroidaceae* among their patients with early pediatric MS²⁷. The relevance of these findings may relate to Lipid 654, a bacterially-derived lipodipeptide produced by a number of *Bacteroidetes* that was found to have lower serum levels among MS patients compared to healthy controls and Alzheimer’s patients^{15, 27}.

Lipid 654 binds toll-like receptor 2 (TLR2)²⁸; although TLRs are critical to innate immune system activation, low-level tonic TLR2 stimulation by Lipid 654 may be immunoregulatory via maintenance of immune system tolerization^{28,29}. Decreased Lipid 654-producing *Bacteroidetes* may therefore be pro-inflammatory, again plausibly linking the gut microbial to MS immunopathogenesis.

Cekanaviciute et al. identified decreased *Parabacteroides distasonis*, which belongs to *Bacteroidetes*, among 51 MS patients compared to 55 controls²⁹. Similarly, Chen et al. identified decreased *Parabacteroides* as well as *Prevotella* among their patients with RRMS compared to controls³⁰. Oral administration of *Parabacteroides distasonis* antigens attenuates experimental murine colitis, with evidence of an immunomodulatory effect on cytokine production and increased mesenteric lymph node CD4+ T-regulatory cells¹⁹. Cekanaviciute et al. found *Parabacteroides distasonis* also augmented the CD4+ T-regulatory cell phenotype, suggesting that it may be linked to MS immunopathogenesis via its influence on CD4+ T-regulatory cell production³¹.

Two studies, the first by Gandhi et al. comparing 53 patients with MS to 44 healthy controls, and the second by Jangi et al. comparing 60 patients with MS to 43 healthy controls, reproducibly found increased *Methanobrevibacter* in the gut microbial of MS patients^{18,19}. Jangi et al. also identified higher breath methane among a cohort of MS patients compared to controls¹⁹, which may be due to increased gut *Methanobrevibacter*. However, the association between increased methane production and constipation is a potential confounder that should be controlled for in future studies, given the high prevalence of constipation in MS^{32,33}. MS patients with antibody reactivity to *Methanobrevibacter*-derived lipids had increased T-cell expression of pro-inflammatory cytokines, and increased *Methanobrevibacter* was associated with reactivity to a myelin sheath component¹⁹. These findings suggest a link between *Methanobrevibacter* and T-cell auto reactivity causing inflammation and demyelination in MS.

Several other differences in the gut microbiota have been identified in MS. Cekanaviciute et al. found that MS patients had increased *Acinetobacter calcoaceticus*, which belongs to *Proteobacteria*³¹. Molecular database analysis identified similarity between *Acinetobacter calcoaceticus* and an encephalitogenic myelin peptide^{34,35}. Elevated anti-*Acinetobacter* antibodies have also been found in MS patients, implicating molecular mimicry as a potential immunopathogenic link between *Acinetobacter* and MS^{35,36}. Cekanaviciute et al. identified a reduction in CD4+ T-regulatory cells after T-cell stimulation with *Acinetobacter calcoaceticus*, suggesting it may also promote autoimmunity by impairing T-regulatory cell function³¹.

Chen et al. found increased abundance of a number of *Proteobacteria* among their patients with RMS, including *Pseudomonas* and *Mycoplana*²⁷. *Proteobacteria* have been associated with IBD by driving inflammation and promoting gut dysbiosis, which may contribute to the development of other autoimmune diseases such as MS³⁷.

Jangi et al. found increased *Akkermansia* among MS patients, which belongs to the phylum *Verrucomicrobia*¹⁹. *Akkermansia muciniphila* has been found to facilitate infection and inflammation by *Salmonella Typhimurium* in gnotobiotic mice³⁸. In contrast, however, reduced *Akkermansia muciniphila* has been observed in IBD and metabolic syndrome³⁹. The implications of increased *Akkermansia* in MS are therefore unclear; there may be a direct immunopathogenic relationship, *Akkermansia* may indirectly facilitate the growth of other pro-inflammatory bacteria, or other mechanisms may contribute. Jangi et al. also found that increased *Akkermansia* and *Methanobrevibacter* positively correlated with expression of genes among T-cells and monocytes implicated in MS pathogenesis; in contrast, butyrate-producing *Butyricimonas* was inversely correlated with these genes, suggesting that gut microflora may contribute to MS pathogenesis by polarizing to an inflammatory rather than immunomodulatory T-cell and monocyte phenotype¹⁹.

Baum et al. noted increased *Bifidobacterium* among MS patients, which belong to *Actinobacteria*³¹. Tremlett et al. similarly found an increase in *Bifidobacterium* among patients with early pediatric MS compared to controls²⁰. *Bifidobacterium*, commonly administered as probiotic therapy, has been linked to IBD⁴⁰. However, *Bifidobacterium animalis* and a probiotic mixture including *Bifidobacterium bifidum* significantly ameliorated EAE activity, with evidence of inhibited Th1/Th17 polarization and regulatory T-cell induction^{41,42}. The reason for this conflicting data regarding *Bifidobacterium* in demyelinating disease is unclear; further study into the potential role of *Bifidobacterium* and other probiotic therapy in MS is needed.

Finally, fecal microbial transplantation is used to treat patients with recurrent *Clostridium difficile* infection (CDI), an antibiotic-associated bacterial colitis that may be life-threatening^{43,44}. Antimicrobial therapy disrupts normal intestinal microflora and facilitates CDI; transplantation of healthy donor stool is believed to restore fecal microbial diversity in the recipient and prevent CDI recurrence^{43,44}. As evidence of gut dysbiosis in MS mounts, FMT from donors free of autoimmune disease may be a consideration to restore microbial balance in those patients. Borody et al. reported neurologic benefit in three MS patients who underwent FMT for constipation⁴⁵. The neurologic improvement was dramatic, including recovery of bowel and bladder function and regained ability to walk. Nevertheless, enthusiasm for these findings is tempered by the absence of controls, the diagnosis of ‘atypical’ MS in two patients, and the unclear biologic plausibility regarding how FMT would reverse established MS disease burden. On this ground, we propose that fecal microbial transplantation from healthy donors to MS patients could restore microbial gut balance and ultimately influence disease activity.

2.4 Pre-clinical studies

Previously reviewed animal research has examined the role of the gut microbiota in experimental autoimmune encephalomyelitis (EAE), a murine model of autoimmune

demyelinating disease⁴⁶. It was shown that germ-free mice devoid of gut microbiota are resistant to EAE, but generally immunodeficient^{47,8}.

The zwitterionic capsular polysaccharide A (PSA) produced by *Bacteroides fragilis* was shown to be protective against EAE, with evidence of a PSA-dependent decrease in the pro-inflammatory cytokine IL-17 and enhanced conversion of IL-10-producing CD4+ T-regulatory cells¹⁶. PSA-mediated induction as well as enhanced immunosuppressive function of human T-regulatory cells has also been shown *in vitro*^{30,49}. PSA uniquely exemplifies a single gut microbial-derived product that has reproducibly demonstrated anti-inflammatory properties and seems protective against immune-mediated demyelination, suggesting therapeutic potential in MS^{30,49}. Furthermore, *Firmicutes* producing the SCFA butyrate are increased in patients assigned to a plant-based rather than animal-based diet, and such SCFAs may have a beneficial anti-inflammatory effect in EAE and MS^{50,51}.

Some probiotic bacteria have been shown to improve EAE, with less pro-inflammatory and increased CD4+ T-regulatory cell responses^{41,42,52-55}. *Bifidobacterium animalis* and a probiotic mixture including *Bifidobacterium bifidum* significantly ameliorated EAE activity, with evidence of inhibited Th1/Th17 polarization and regulatory T-cell induction^{41,42}. Whether there is any benefit to dietary probiotic supplementation in MS, however, is unknown, and caution may even be warranted given increased *Bifidobacterium* was identified in some MS gut microbiome studies for example.^{26,31}

The use of antibiotics to reduce the gut bacterial load is protective against EAE, with reduced pro-inflammatory cytokine production and enhanced CD4+ T-regulatory cell proliferation^{30,48}. Yokote⁵⁶ et al. studied the possible effects of altering gut flora by antibiotic treatment on EAE. First, mice treated with kamamicina, colistina and vancomycin (KCV) had a change in their gut flora compared to the control group proved by DNA microarray analysis after KCV. The experimental mice group was treated starting one week before immunization. After the EAE induction, the experimental group had less clinical manifestations, less mononuclear cells infiltrations on lumbar spinal cord and reduced demyelination compared to the control group. Moreover, they also studied the cells response *in vitro* with antigen stimulation. Interestingly, the proliferation response of the mononuclear cells were not affected in the experimental group but they produced less inflammatory cytokines (IL-6 and 17) and showed a reduced expression of ROR, an important transcription factor for Th17, together with enhanced production of IL-10.

In summary, animal models suggest that the gut microbiota can powerfully modulate immune-mediated demyelination. Moreover, that inflammatory cytokines can be influenced by microbiota changes in a measurable fashion.

2.5 Rationale for the use of FMT for the treatment of multiple sclerosis patients

Gastrointestinal disorders have more data published in the literature on this matter. A recent systematic review by Chapman et al. of FMT for CDI included 29 studies, 2 of them randomized control trials, 4 prospective and 23 retrospective. The authors concluded that FMT is a highly effective therapy for refractory or recurrent CDI with a success rate of 83-100% with an acceptable safety profile⁵⁷. Another systematic review and meta-analysis by Sun et al. of FMT for ulcerative colitis (UC) identified 2 RCTs, 1 open-label case-control study, and 8 non-control cohort studies about the efficacy and safety of FMT in UC patients. They concluded that FMT may be an efficacious and safe alternative therapy for UC, at least when the standard therapy has failed or is unacceptable⁵⁸.

FMT has also been studied in metabolic disorders by Vrieze et al. This was a double-blind, randomized controlled study where half of the 18 male patients with metabolic syndrome were transplanted their own feces (control group), while the other half were transplanted feces from thin donors (experimental group). The experimental group showed significant increase in insulin sensitivity after six weeks from FMT⁵⁹.

Fecal matter transplantation in patients has been tested in a few medical conditions. Most reports consist in open label or non-controlled studies with a small number of subjects. Moreover, the fecal matter transplant may vary the way the transplant is prepared as the route of administration which makes comparisons even harder. Even though more robust evidence about the efficacy and application of this procedure is lacking, one can conclude that FMT is feasible and safe for a phase II clinical study.

The rationale for treatment of MS patients with FMT in a phase II study is to restore a gut microbiome composition to one similar to a healthy person, and measure its possible effects in biomarkers as pro and anti-inflammatory cytokines related to MS pathophysiology. We plan to further study gut bacteria interaction in MS by DNA blood bacteria and gut permeability analysis.

2.6 Patient population and study rationale

This is essentially an immunological study, and therefore patients with RMS, regardless of the disease duration, will be enrolled in this study. They will be in a standard of care treatment for their MS and may or may not be on treatment with disease modifying therapy as per their own individual case. On the other hand, patients must be off of systemic high dose corticosteroids for at least 90 days.

The primary aim of this study is to determinate if FMT can affect the immunological cytokine profile of MS patients. We also aim to evaluate the safety and tolerability of this treatment in this population. To our knowledge, a study like this has not yet been published anywhere else in the world.

2.7 Potential risks for FMT and study procedures

Two randomized control Trials (RCTs) reported mild adverse events attributed to FMT, including diarrhea, cramping, belching, nausea, abdominal pain, bloating, transient fever, and dizziness⁴¹. Serious adverse events were also described, including a case of Fournier gangrene⁶¹, but none were attributed to the FMT.

Eight case-series studies (reporting on 70 patients) did not explicitly mention harms; all others specifically commented on harms (or lack thereof). Possible procedure-related harms, including micro perforation with colonoscopy⁶² and gastrointestinal bleeding⁶³, peritonitis⁶⁴, and pneumonia⁶⁴ with use of the upper gastrointestinal tract route, were rarely reported. One case-series study reported on FMT use in 80 immuno compromised patients⁶⁵. Although serious adverse events (2 deaths and 10 hospitalizations) occurred in 12 patients (15%); 4 were considered related to FMT, and 5 were possibly related.

Because rare adverse events may be first reported as a case report, we examined case reports for such events. One report⁶⁶ described a patient with abdominal pain and hypotension 3 days after FMT by means of a gastro jejunostomy tube placed through an indwelling gastric tube. The patient had pneumoperitoneum, toxic megacolon, and polymicrobial bacteremia and subsequently died. Long-term data on harms were not reported.

According to published articles, transient adverse responses after FMT have been reported, including mild fever, abdominal pain, diarrhea, exhaust, flatulence, and fatigue. However, these adverse effects are self-limiting. De Leon et al⁶⁶ reported a UC patient quiescent for more than 20 years who developed a flare of UC after FMT. This case gives us cautionary information concerning FMT being used to treat CDI with UC. Moreover, a recent paper reported a UC patient who had a cytomegalovirus infection after performing home FMT without donor screening⁶⁷. As extracts of feces are mediators between the donor and recipient, FMT has the potential for transmitting occult infections even when strict donor screening is performed.

More recently Wang et al published a systematic review on safety of FMT. A total of 50 studies including original full-text articles, letters to the editor, abstracts of scientific conferences, case reports and case series which were published between 1913 and 2015 were reviewed. Totally 78 kinds of AEs were revealed with a total incidence rate of 28.5%. Among the 42 publications, 5 kinds were definitely and 38 kinds were probably related to FMT. The commonest FMT attributable AE was abdominal discomfort, which was reported in 19 publications. For upper gastrointestinal routes of FMT, 43.6% (89/204) patients were compromised by FMT-attributable AE, while the incidence dropped to 17.7% (76/430) for lower gastrointestinal routes. In contrast, the incidences of serious adverse events (SAEs) were 2.0% (4/196) and 6.1% (40/659) for upper and lower gastrointestinal routes, respectively. A total of 44 kinds of SAEs occurred in 9.2% patients, including death (3.5%, 38/1089), infection (2.5%, 27/1089), relapse of inflammatory bowel diseases (0.6%, 7/1089) and *Clostridium difficile* infection (0.9%, 10/1089).

The paucity of RCTs is notable. As a result, there is a dearth of high-quality evidence to guide clinicians and policymakers on how to apply this promising but largely untested therapy. The overall low quality of the available evidence evaluating FMT is important and indicates that additional research is needed. However, the information available suggests that FMT can be safely done.

3. STUDY OBJECTIVES AND PURPOSE

This is a prospective, cross-over, open label, randomized 1:1 early vs delayed groups, interventional [FMT] vs treatment as usual controlled trial to explore the effects of FMT from a healthy donor to RMS patients and investigate whether this can influence disease activity based on a panel of biological markers.

3.1 Primary outcome

To evaluate if FMT from healthy donors can significantly change cytokine profile in peripheral blood samples of RMS patients.

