6.2.3 Peripheral blood cytokines levels

Cytokine levels will be measured as previously described⁷². Peripheral blood will be collected into EDTA blood collection tubes ensuring complete mixing with anticoagulant to avoid clotting. Within 60 minutes of blood collection samples will be spun for 10 minutes at 4500xg. The plasma will be collected and aliquoted into cryovials. All samples will be collected and stored at -80°C before the plasma is measured for 25 immunological cytokines using a luminex-based multiplexed immunoassay. The Human Th17 Magnetic bead panel (HTH17MAG-14K, Millipore) will be used in this study to detect changes in Interleukin 1 β (IL-1 β), IL-2, IL-4, IL-5, IL-6, IL-9, IL-10, IL-12p70, IL-13, IL-15, IL-17A, IL-17E/IL-25, IL-17F, IL-21, IL-22, IL-23, IL-27, IL-28A, IL-31, IL-33, granulocyte macrophage colony stimulating factor (GM-CSF), interferon γ (IFN γ), macrophage inflammatory protein 3 α (MIP-3 α), tumour necrosis factor α (TNF α) and TNF β . Plasma samples will be run in duplicate and assays will be standardized as per product specifications. Plasma cytokine levels in healthy controls will be compared to levels in MS patients at all time points. Moreover, cytokine levels of MS patients at baseline (D0) will be compared to levels at 12 months to determine whether intervention (FMT) had an effect on pro- and anti-inflammatory cytokine levels.

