6.3 Sample Size analysis

It was assumed that the acceptable Type I error will be 0.05 and power will be 0.8. Moderate effect size effect is expected. This is a study of a kind that has never been done before in this population. From similar studies in other populations or other interventions on a similar population, a 40% change in cytokine levels (ie TGFbeta1) analysis is expected, as reported on other cytokine study with no pharmacological intervention, such as vitamin D supplementation⁷³.

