7.0 ASSESSMENT OF EFFICACY

As this study is an immunological study, the following efficacy outcomes will be evaluated:

- Changes in peripheral blood cytokines within RMS patients between baseline and months 1 to 12 inclusive, for both groups. Luminex kit will be used.
- Changes on microbiome after FMT by analyzing the gut bacterial composition through stool analysis and blood bacteria DNA at baseline, and months 1 to 12 inclusive for both groups.
- Gut permeability through urine analysis at baseline, 6 and 12 months for both groups.

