9.3 Biomarkers

We will analyze mean differences between two independent groups whilst subjecting participants to repeated measures overtime to assess variability between- and within-subjects variable. Therefore, we will use the mixed-design ANOVA model.

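### The comparison that section 6.2.3 uses to judge an FMT effect on cytokines (baseline vs month 12) has no untreated control and conflicts with 9.3, and no primary contrast, analyte or multiplicity rule is set for 25 cytokines

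*Combined protocol and SAP*

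**What the plan says.** - **Question.** Section 3.1 sets the primary outcome: "To evaluate if FMT from healthy donors can significantly change cytokine profile in peripheral blood samples of RMS patients". The synopsis objective covers baseline to as late as 12 months and singles out no time point.
- **Measurements.** In 6.2.3, samples are stored "before the plasma is measured for 25 immunological cytokines using a luminex-based multiplexed immunoassay". Blood is drawn at baseline and at every month from 1 to 12 in both groups (Tables 1 and 2).
- **Comparisons.** Section 6.2.3 states that "cytokine levels of MS patients at baseline (D0) will be compared to levels at 12 months to determine whether intervention (FMT) had an effect", and also that "Plasma cytokine levels in healthy controls will be compared to levels in MS patients at all time points". Section 7.0 lists as an efficacy outcome "Changes in peripheral blood cytokines within RMS patients between baseline and months 1 to 12 inclusive, for both groups". Section 9.3, the only cytokine analysis in the statistical section, says: "We will analyze mean differences between two independent groups whilst subjecting participants to repeated measures overtime", using a mixed-design ANOVA.
- **Error rate.** Section 6.3: "It was assumed that the acceptable Type I error will be 0.05". It is tied to no test. The one cytokine named there ("a 40% change in cytokine levels (ie TGFbeta1) analysis is expected") is not among the 25 in 6.2.3.
- **FMT schedule.** The early group receives FMT at baseline and months 1 to 5, the late group at months 6 to 11. Section 6.2.2 places each visit's blood sample before that visit's FMT.
- **Status.** Section 3 describes an exploration of effects on a panel of markers. Section 9.1 calls the study an exploratory proof of concept.
- **Population and missing data.** Section 9.7 analyses patients with one week of study treatment. Section 9.6 allows no imputation.

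**The concern.** The trial randomises 40 patients and keeps one group untreated for six months. That is what allows an FMT effect to be separated from season, assay drift, regression to the mean or changes in background MS therapy. Yet the comparison that 6.2.3 assigns to judging an FMT effect does not use that group. Section 9.3 points the other way, and no passage says which prevails.

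The success criterion is also open. Section 3.1 asks for a significant change in a profile, but the plan does not say which cytokine, how many cytokines, or which model term would establish one. The contrast, the analyte and the rule could all be chosen after the data are seen.

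**Working it through.** The plan states no figure that depends on the choice of contrast (9.1 says the group size was arbitrary), so there is none to reproduce. All drifts, correlations and effect sizes below are assumptions; the documents give none.

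**1. Exposure at month 12.** Early group: six FMTs, the last at month 5, so 12 − 5 = 7 months earlier. Late group: six FMTs, the last at month 11, so 12 − 11 = 1 month earlier. Baseline vs month 12 therefore has no untreated comparator and mixes two very different intervals since treatment.

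**2. Exposure at month 6.** Early group: six FMTs, the last 1 month earlier. Late group: none, because the month-6 sample precedes its first FMT. This is the last randomised treated-vs-untreated comparison.

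**3. Which term in 9.3 matters.** Suppose FMT shifts a cytokine by δ only in the sample one month after each FMT. Over the 13 samples the early group averages 6δ/13 (months 1 to 6) and the late group also 6δ/13 (months 7 to 12). The group main effect over the year is then 6δ/13 − 6δ/13 = 0. So 9.3 answers 3.1 only once a term and a period are named.

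**4. Cost of the uncontrolled contrast.** No FMT effect, common drift 0.2 SD, visit-to-visit correlation r, paired t test at two-sided 0.05. Noncentrality = 0.2/√(2(1−r)) × √n.

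| r | noncentrality, n = 40 | rejection, 40 pooled | rejection, 20 in one group |
|---|---|---|---|
| 0.3 | 1.069 | 0.18 | 0.11 |
| 0.5 | 1.265 | 0.24 | 0.14 |
| 0.7 | 1.633 | 0.36 | 0.20 |

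The randomised contrast stays at 0.05, because a common drift cancels between groups.

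**5. Twenty-five tests of one contrast.** If each cytokine is tested at 0.05 and any one suffices, independence gives 1 − 0.95^25 = 0.723. Simulated two-sample t tests (20 vs 20, equal pairwise correlation, no true effect) give about 0.61, 0.48, 0.33 and 0.17 at correlations 0.3, 0.5, 0.7 and 0.9.

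**6. Month 6 or an average of months 1–6.** Two-sample t test, 20 per group, alpha 0.05, d in single-visit SD units. The SD of a six-visit mean is √((1+5r)/6): 0.866 at r = 0.7 and 0.645 at r = 0.3.
- Month 6 alone, d = 0.5: power 0.34.
- Average, full effect from month 1: effective d = 0.5/0.866 = 0.577 and 0.5/0.645 = 0.775; power 0.43 and 0.67.
- Average, effect rising linearly to 0.5 at month 6: mean effect 0.5 × 3.5/6 = 0.292; effective d 0.337 and 0.452; power 0.18 and 0.29, below month 6 alone.

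**7. Price of adjustment.** At the Bonferroni level 0.05/25 = 0.002, month-6 power falls from 0.34 to 0.05 at d = 0.5 and from 0.69 to 0.24 at d = 0.8. Benjamini-Hochberg at 5% rejects everything Bonferroni does, so these are floors for it. Baseline adjustment, not included here, would raise power.

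**The case against.** The best defence is that the study is exploratory (sections 3 and 9.1), so 25 markers need no strict error control, and that 9.3, as the statistical section, governs over a laboratory section such as 6.2.3. The first part largely stands: reporting all 25 as estimates would be acceptable. But 3.1 asks for a significant change, 4.1 speaks of statistical significance and 6.3 sets a type I error, so the plan is not written consistently as exploratory. The second part is reasonable but stated nowhere, and 9.3 still leaves its deciding term open. Exploratory status does not make an uncontrolled contrast a test of FMT.

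Three stronger readings are tempting, and the documents do not support them.
- **Four rival primary analyses.** Section 7.0 can be read as naming the outcome and 9.3 as its model. The synopsis makes the healthy volunteers a reference arm, seen once. The real conflict is between 6.2.3 and 9.3.
- **A 72% false-positive risk.** That needs independent cytokines and an any-one-suffices rule. The plan states neither, and the word profile does not imply the rule.
- **The randomised control goes unused.** Section 9.3 does compare the groups; what is missing is its designation as the answer to 3.1.

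The drift figures also depend on an unsourced 0.2 SD and on pooling 40 patients; tested per group they are 11% to 20%. The point about 9.7 rests on a literal reading. If study treatment includes standard care, no late-group patient is lost by that rule.

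**Conclusion.** The point holds in this form. The within-patient comparison in 6.2.3 cannot separate an FMT effect from a time shift common to both groups. It conflicts with 9.3, and nothing settles which contrast, term, period, analyte or rule answers 3.1. That much follows from the text and the FMT schedule alone.

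The size is conditional. Under the stated assumptions, false rejection for one cytokine from a modest common drift is 11% to 36%, against 5% for the randomised contrast. The any-of-25 error for one contrast is about 0.17 to 0.72 as correlation falls from 0.9 to 0. These figures show what the plan leaves open, not what the trial will do. The plan should be amended; given its exploratory status this is not a fatal flaw. Confidence in the textual finding is high.

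**What to change.** Before any cytokine data are examined, amend 3.1, 6.2.3, 7.0, 9.3, 9.7 and the synopsis objective together.

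1. **Primary contrast.** Make it the randomised early-vs-late comparison up to the pre-FMT month-6 sample. State the term and time point: the group difference at month 6, or the group-by-time effect over months 1–6. Avoid a plain average of months 1–6 if the effect is expected to build gradually.
2. **Model and population.** Use a likelihood-based linear mixed model adjusted for the baseline cytokine level. A classical mixed-design ANOVA needs complete data, and 9.6 bars imputation; the mixed model lets incomplete patients contribute without it. Include all randomised patients with cytokine data. Read literally, 9.7 drops late-group patients who leave before month 6 but keeps their early-group counterparts.
3. **Other comparisons.** Label baseline-to-month-12, the other within-patient changes and the healthy-volunteer comparison descriptive.
4. **Claim.** Choose one. Either keep the claim of significance in 3.1, with Benjamini-Hochberg at 5% across the 25 cytokines and a definition of a changed profile, or with one cytokine from the 6.2.3 panel named as primary. Or, in line with 9.1, report all 25 as exploratory estimates with intervals and remove the claim from 3.1.

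The cost is wording only: no new visits or samples. Adjustment loses power per cytokine (the floors are in the working). One named cytokine avoids the loss but allows no claim for the other 24. The exploratory route avoids it but gives up the claim of significance.
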